4.1 Inclusion Criteria

1. Patients diagnosed with chronic rhinosinusitis, with and without polyps, as well as allergic fungal sinusitis
2. Patients who have undergone Functional Endoscopic Sinus Surgery (FESS)
3. Purulent drainage on nasal endoscopy
4. Male or female subjects, 18 years of age or older
5. Patients seen at the Dept. of Otorhinolaryngology clinic at HUP, a tertiary care clinic.

4.2 Exclusion Criteria

1. Pregnant women
2. Immunocompromised patients
3. Granulomatous diseases with rhinologic manifestations (Wegner's, Sarcoid, Churg-Strauss)
4. Primary ciliary dyskinesia

4.3 Subject Recruitment and Screening

All study personnel will be appropriately trained and certified according to their role in the study and duties, including HIPAA and CITI training.

Subjects will be identified and approached as they present to clinic for their routine treatment for chronic rhinosinusitis. Subjects will be brought into a private clinical examination room where a clinical research nurse will explain the protocol in detail. Subjects will have the time to ask and have questions answered about the research prior to signing the consent form.

Patients interested in enrolling in the study will be instructed on how to administer the solutions using a 3cc syringe with an atomizer and have the opportunity to trial this technique with isotonic buffered saline under direct supervision of the treating physician or research coordinator. Patients who feel that they can adequately self-administer the solution will be asked to participate in the study.

Subjects who withdraw or are otherwise not interested in the protocol will have access to the ENT clinic for their regular care. They will be reminded that their care (and if applicable, employment, or student status at Penn) will in no way be affected by their decision to participate in the protocol or not.

As per FDA recommendation, the first 10 patients enrolled into the study will be placed into the treatment arm, and will not be randomized. The purpose of this is to make sure that the treatment is efficacious enough to rationalize going forward with the trial. This will not affect the ICF, as the patient will not be aware of this forced assignment into the treatment arm (i.e. they will still be blinded to their assignment).

CONFIDENTIAL

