6.1 Visit 1 (week 0)

Patients who consent to participate will be randomized to a treatment arm of quinine and saline (1mg/ml) or sucrose octaacetate (0.5mg/ml) in saline as dispensed by IDS. The study nurse coordinator will instruct the patient on how to administer the solution.

Following the routine endoscopically guided sinus culture swab, an additional research microbiome swab will be obtained. Patients will be asked to complete a routine Sinonasal Outcomes Test (SNOT-22) questionnaire as well as undergo a Sniffin' Stick Test as part of the research. Additionally, as part of their initial clinical assessment, a nasal endoscopy will be performed and recorded. This will later be scored by a blinded clinical investigator. If a CT scan of the sinuses is clinically indicated, then one will be performed. Additionally, a taste test to determine bitter taste sensitivity will be administered. This taste test is comprised of non-toxic solutions which are not swallowed by the patient.

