9.2 Auditing and Inspecting

The Investigator will permit study-related monitoring, audits, and inspections by the Sponsor, EC/IRB, government regulatory bodies, and University compliance and quality assurance groups of all study related documents (e.g. source documents, regulatory documents, data collection instruments, study data etc.). The investigator will ensure the capability for inspections of applicable study-related facilities (e.g. pharmacy, diagnostic laboratory, etc.).

Participation as an investigator in this study implies acceptance of potential inspection by government regulatory authorities and applicable University compliance and quality assurance offices.

10 Ethical Considerations

This study is to be conducted accordance with applicable US government regulations and international standards of Good Clinical Practice, and applicable institutional research policies and procedures.

This protocol and any amendments will be submitted to a properly constituted independent Ethics Committee (EC) or Institutional Review Board (IRB), in agreement with local legal prescriptions, for formal approval of the study conduct. The decision of the EC/IRB concerning the conduct of the study will be made in writing to the investigator and a copy of this decision will be provided to the sponsor before commencement of this study. The investigator should provide a list of EC/IRB members and their affiliate to the sponsor.

All subjects for this study will be provided a consent form describing this study and providing sufficient information for subjects to make an informed decision about their participation in this study. See Attachment for a copy of the Subject Informed Consent Form. This consent form will be submitted with the protocol for review and approval by the EC/IRB for the study. The formal consent of a subject, using the EC/IRB-approved consent form, must be obtained before that subject undergoes any study procedure. The consent form must be signed by the subject or legally acceptable surrogate, and the investigator-designated research professional obtaining the consent.

11 Study Finances

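### Section 4.3 leaves the consent form unchanged for 10 non-randomized quinine patients on the ground that they are blinded; that reason does not hold, and Section 6.1 contradicts it

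*Combined protocol and SAP*

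**What the plan says.** Section 4.3 (Subject Recruitment and Screening) attributes a lead-in to an FDA recommendation: "the first 10 patients enrolled into the study will be placed into the treatment arm, and will not be randomized". It gives the aim: "The purpose of this is to make sure that the treatment is efficacious enough to rationalize going forward with the trial". On consent it adds: "This will not affect the ICF, as the patient will not be aware of this forced assignment into the treatment arm". The same section says that, before signing, "a clinical research nurse will explain the protocol in detail".

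Other sections describe the trial differently:

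- Section 6.1 (Visit 1): "Patients who consent to participate will be randomized to a treatment arm of quinine and saline (1mg/ml) or sucrose octaacetate (0.5mg/ml) in saline". It makes no exception for the lead-in.
- Section 10 (Ethical Considerations) promises every subject a "consent form describing this study and providing sufficient information for subjects to make an informed decision about their participation in this study". Again there is no exception.
- Section 7.5 (Stopping Rules) tells the attending physicians the assignment of the first 10 participants and has them use the outcomes to decide whether the trial proceeds.
- Section 3.1 labels the whole protocol as randomized and blinded on both sides, and Section 5.3 has the very first patient assigned by simple randomization.

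**The concern.** The first 10 patients differ from the rest in three ways: how they are assigned, who knows the assignment, and what their data are used for. The protocol does not overlook the consent form here. It states that the form need not change and gives a reason, namely that the patient will not know.

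That reason runs two things together. Blinding withholds from a patient which arm they are in. A consent form tells a patient how arms are assigned. The first does not require silence about the second.

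At stake is whether patients in the group that informs the proceed/abort decision were told about an arrangement that applies to them. A protocol that says both that everyone is randomized and that 10 are not also leaves an IRB or a later reader unsure which account the form follows.

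**Working it through.** **Inputs.** From Section 4.3: 10 patients, certain assignment to quinine. From Section 6.4: 100 patients in total, SD 20 for SNOT-22, target half-width 10 for the 95% confidence interval, 32 per group. From Section 5.3: urn randomization, with no ratio or urn parameters stated. Equal allocation (p = 0.5) is therefore an assumption. Section 6.4 supports it by sizing two equal groups, and Section 5.3 by describing a rule that pulls the arms toward balance.

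**The plan's own figure.** The point does not depend on the sample size, but the figure reproduces.

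- Normal formula: 2 × (1.96 × 20 / 10)² = 30.7, rounded up to 31.
- With the t distribution, the smallest n per group for which t(0.975, 2n − 2) × 20 × √(2/n) is at most 10 is 32, where the half-width is 9.99.

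Describing only the remaining 90 patients as randomized does not threaten that target. With 45 per arm the half-width is 8.4, against 7.9 with 50 per arm.

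**Size of the departure.**

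- Share of patients affected: 10 / 100 = 10%.
- Probability of quinine: 1.0 in the lead-in against p under randomization. At p = 0.5 the gap is 1.0 − 0.5 = 0.5. If the unstated ratio were 2:1 for quinine, p = 2/3 and the gap is 1/3; at 1:2 it is 2/3. The gap is zero only if nobody can receive placebo.
- Chance that independent equal randomization would put all 10 on quinine: 0.5¹⁰ = 0.001. Under the urn rule it is smaller still, because each quinine assignment lowers the chance of the next. The lead-in cannot be read as a variant of the described randomization.

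**The texts side by side.**

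1. Section 4.3 against Section 6.1. One says the first 10 are not randomized; the other says that all who consent are. Both cannot be true of the same 10 people, so this is a direct contradiction.
2. Section 4.3 against Section 10. Section 10 asks for a form that describes the study and is sufficient for an informed decision. A form unaffected by the lead-in would, on its face, not describe the lead-in. This is tension with a general clause. Section 10 contains no sentence requiring the allocation method or probability to be disclosed.
3. Section 4.3 against itself. It promises a detailed explanation of the protocol before signing, yet rests the unchanged form on the patient's unawareness. Whether the nurse's explanation covers the lead-in is not stated.
4. Section 4.3 against Section 7.5. Section 4.3 makes the lead-in a check of efficacy. Section 7.5 speaks of efficacy but then makes continuation depend on adverse events in the treatment and/or placebo arms, although the first 10 include no placebo patient. The passages must be reconciled before anyone can say exactly which data the decision uses.

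**Does blinding require the omission?** No. A form can say that some participants are assigned without randomization and that nobody is told whether they are among them. Each patient's own arm stays undisclosed. The protection weakens if the wording identifies the earliest enrollees, because an early patient could then infer the arm.

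**The case against.** The strongest reply is that the consent form cannot be read here. Section 10 refers to it as an attachment, and consent pages are not in the review copy. The sentence in Section 4.3 shows only that the lead-in was not treated as a reason to alter the form. It does not show that the form promises randomization or a one-in-two chance. This stands, and it limits the conclusion. It does not rescue Section 4.3, though: if the form already discloses the lead-in, that section's rationale is wrong and should go anyway.

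Other replies stand in part:

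- The lead-in is attributed to the FDA, so it should not be presented as the investigators' own idea. But the recommendation is cited for the assignment; the reason given for the unchanged form is patient unawareness.
- Section 10 leaves approval of the form to the EC/IRB, which receives it with the protocol. Sufficiency is that body's judgment. The documents record no waiver or approval of incomplete disclosure.
- Anyone who consents accepts possible quinine, and Section 1.5 puts the maximum daily exposure (12 mg) below that in a glass of tonic water (19.6 mg). The kind of exposure is unchanged; its probability, and the unblinding of the physicians, are not.
- Disclosure could let patients guess their arm, and SNOT-22, a primary outcome, is self-reported. This is a real cost and shapes the wording of the fix.

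A reader might infer more: that consent was defective, that information was hidden with intent, that the lead-in data are unusable, or that the trial would be halted. The documents support none of these. The form's text is missing, the protocol gives a reason but shows no motive, and no passage addresses what an adverse ethics finding would do to the data.

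**Conclusion.** The point holds in a limited form. The reason Section 4.3 gives for leaving the consent form alone is not a valid one, because blinding to one's own arm does not justify leaving the allocation scheme undisclosed. Section 4.3 directly contradicts Section 6.1 and fits poorly with Section 10, without breaching any express disclosure requirement there.

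It affects 10 of 100 patients, whose probability of quinine is 1.0 against about 0.5 under an assumed equal allocation. These patients also feed the Section 7.5 decision, although its mention of a placebo arm means one cannot say that they supply all the data for it.

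Whether consent is actually defective cannot be determined without the form. Invalid data or a halted trial is a possibility only. The change is worth making because it protects participants at small cost.

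**What to change.** 1. In Section 4.3, delete the sentence that says the consent form is unaffected because the patient will not know.
2. In the single form used for all subjects, add one sentence: some participants are assigned to the study drug without randomization, their physicians may know this, and participants are not told whether they are among them. Do not say that these are the earliest enrollees.
3. Correct Section 6.1 so that only subjects after the lead-in are described as randomized, and make clear that the urn scheme in Section 5.3 starts there.
4. Reconcile Sections 4.3, 6.1, 7.5 and 10 on who is randomized, who is unblinded, and which data inform the proceed/abort decision.
5. Submit the changes to the IRB, with the current form wording, so that the IRB can judge whether disclosure is sufficient. The documents do not say whether enrollment has begun; if it has, what to tell subjects already in the lead-in is for the IRB to decide.

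**Cost.** One IRB amendment, one sentence in the form and short protocol edits, with no change to the target sample size. Some patients may guess their arm, which could color self-reported SNOT-22 scores; the general wording keeps that risk small but does not remove it.

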4.4 Early Withdrawal of Subjects

4.4.1 When and How to Withdraw Subjects

Subject may be withdrawn from the study prior to the expected completion of the protocol if the subject fails to adhere to protocol requirements, subject withdraws consent, or symptoms of acute rhinosinusitis exacerbation persist. Subjects will return to routine clinical care at that point.

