2.1 Primary Outcome Variable(s)

CONFIDENTIAL

The primary outcomes variables are:

- Pre- and post-treatment endoscopically guided sinonasal microbiologic cultures
- Pre- and post-treatment nasal endoscopy scored with the Lund-Kennedy scoring system by a blinded investigator¹⁸.
- Pre- and post-treatment quality of life questionnaires (22-item Sinonasal Outcomes Test [SNOT-22]).
- The necessity for rescue oral antibiotics for persistent infection.

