4.4.2 Data Collection and Follow-up for Withdrawn Subjects

Even though subjects may be prematurely withdrawn from the study, it is imperative to collect infection data (microbiology swabs) or symptomatic data. Such data is important to the integrity of the final study analysis since early withdrawal could be related to the tolerability profile or the ineffectiveness of the therapy. If a subject withdraws consent to participate in the study, attempts should be made to obtain permission to follow up with the subject's CRS for the duration of the 12-week follow-up period. Subjects with incomplete/missing data will not be included in the analysis.

5 Study Drug

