6.5 Statistical Methods

Data will be analyzed after 100 subjects have completed the study. Descriptive demographic data will be compiled including mean and median age, adjuvant therapy use, use of oral antibiotics, and microbiome profile. Longitudinal linear mixed effects modeling will be used to examine the relationship between all outcome measures and treatment assignment, assuming that the distribution of the outcome measures follow a unimodal symmetric distribution and satisfies the assumptions for mixed effects modeling. Mixed effects modeling takes advantage of all available data (up to the point of loss to follow-up or withdrawal) and also can address missing data. As long as the level of missingness is not excessive and patterns of missingness are not detected, mixed effects modeling can use all available data.²¹⁻²⁴ For all analyses, alpha will be set to 0.05 (two-sided).

The Epidemiology Department may be consulted at the completion of the study to assist with data analysis. Only de-identified data will be provided. No PHI will be shared.

CONFIDENTIAL

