6.6 Subject Population(s) for Analysis

All-randomized population: Any subject randomized into the study, regardless of whether they received study drug, will be analyzed.

7 Safety and Adverse Events

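### The rule in 4.4.2 that drops subjects with incomplete data contradicts 6.5 and 6.6, and lets exclusion from the primary analyses depend on outcome

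*Combined protocol and SAP*

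**What the plan says.** Section 4.4.1 lists the grounds on which a subject may be withdrawn from the study: "subject fails to adhere to protocol requirements, subject withdraws consent, or symptoms of acute rhinosinusitis exacerbation persist". Withdrawn subjects go back to routine care.

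Section 4.4.2 recognises that withdrawal can carry information about treatment, since "early withdrawal could be related to the tolerability profile or the ineffectiveness of the therapy". For prematurely withdrawn subjects it says "it is imperative to collect infection data (microbiology swabs) or symptomatic data". It closes with the opposite instruction: "Subjects with incomplete/missing data will not be included in the analysis". It does not say which outcome or visit must be missing for a subject to count as incomplete.

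Section 6.5 says that mixed modelling "takes advantage of all available data (up to the point of loss to follow-up or withdrawal", provided that missingness is not excessive and "patterns of missingness are not detected". Section 6.6 defines the analysis population: "Any subject randomized into the study, regardless of whether they received study drug, will be analyzed".

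The four primary outcomes in 2.1 are culture, Lund-Kennedy endoscopy, SNOT-22 and "The necessity for rescue oral antibiotics for persistent infection". Under 3.2 the antibiotic endpoint covers use both during and after irrigation.

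**The concern.** There are two linked problems.

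First, the plan holds two incompatible rules on who is analysed. Two analysts following the same document would use different subjects, and the choice could be made after unblinding.

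Second, the exclusion rule is not neutral with respect to outcome. Lack of efficacy can lead to withdrawal, withdrawal can leave later visits missing, and under 4.4.2 a missing visit removes the whole subject, including any week-4 data. The groups compared would then no longer be the groups as randomized. The mixed model does not rescue this: 6.5 relies on there being no detected pattern of missingness, whereas 4.4.1 permits a pattern by rule, and 4.4.2 would discard the pre-withdrawal data that the model could have used.

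**Working it through.** **Which rule keeps which subject**

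| Subject | 4.4.2, read literally | 6.5 and 6.6 |
|---|---|---|
| Randomized, baseline and week 4 complete, withdrawn for persistent symptoms, no week 12 | Out | In, with data to week 4 |
| Randomized, rescue antibiotics recorded, later visits missing | Out, although the rescue was observed | In |
| Randomized, pus cleared, no follow-up traditional swab | Out (culture missing) | In |
| Randomized, all visits attended, no CT because none was clinically needed | Out (secondary outcome missing) | In |

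The first two rows remove failures. The third removes successes: the footnote in 3.1 makes the traditional swab depend on visible pus, although the section 6 table lists the culture at every visit without that condition. The fourth row follows from 2.2 and 3.3, where CT is done only on clinical grounds.

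**The plan's own figure.** Section 6.4 gives 32 per group for a 95% CI half-width of 10 with SD 20. Half-width = t(0.975, 2n−2) × 20 × √(2/n). At n = 32 this is 1.999 × 20 × 0.25 = 9.99, so the figure reproduces. At 50 per arm the half-width is 7.9.

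**Illustration for SNOT-22.** The documents give no failure or withdrawal rates, so these inputs are assumptions:
- change in SNOT-22 is normal with SD 20 (the SD in 6.4, assumed to apply to change), lower being better;
- mean change is 0 on placebo and −10 on quinine; the 10 borrows the precision in 6.4 and is not an effect that the plan expects;
- failure is a change above one common cutoff c, set so that 40% of placebo fails: c = 20 × 0.2533 = 5.07.

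For arm mean μ, let a = (c − μ)/20. The mean among successes is μ − 20φ(a)/Φ(a), and among failures μ + 20φ(a)/(1 − Φ(a)).

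- Placebo: a = 0.253, 40.0% fail, success mean −12.88, failure mean 19.32.
- Quinine: a = 0.753, 22.6% fail, success mean −17.76, failure mean 16.63.

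If a share w_F of failures and w_S of successes is excluded in both arms, the analysed mean is [(1 − w_S)Φ(a) × success mean + (1 − w_F)(1 − Φ(a)) × failure mean] / [(1 − w_S)Φ(a) + (1 − w_F)(1 − Φ(a))].

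| Excluded in both arms | Placebo mean | Quinine mean | Difference |
|---|---|---|---|
| None | 0.00 | −10.00 | 10.0 |
| 25% of failures | −2.15 | −11.59 | 9.4 |
| 50% of failures | −4.83 | −13.39 | 8.6 |
| 100% of failures | −12.88 | −17.76 | 4.9 |
| 25% of successes | 2.27 | −8.14 | 10.4 |
| 50% of successes | 5.52 | −5.10 | 10.6 |
| Equal share of both | 0.00 | −10.00 | 10.0 |

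With 20% placebo failure (9.0% on quinine), excluding 25%, 50% or 100% of failures gives 9.4, 8.6 or 6.6.

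**Illustration for rescue antibiotics.** Assume true rates of 40% on placebo and 20% on quinine, with a share s of rescued subjects excluded. The observed rate is p(1 − s)/(1 − ps). At s = 0.25 this is 33.3% v 15.8%, a difference of 17.5 points; at s = 0.5 it is 25.0% v 11.1%, or 13.9 points. The true difference is 20 points. The odds ratio stays at 2.67.

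**No true effect.** Equal exclusion gives no bias in the difference. Unequal exclusion does: with a true 30% rescue rate in both arms, excluding 80% of rescued subjects in one arm and 40% in the other gives 7.9% v 20.5%, a false difference of 12.6 points.

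**The case against.** The best defence is that this is one badly worded sentence in a follow-up section, which the sections that specify the analysis would override. Withdrawal is discretionary, and 4.4.2 itself insists on collecting data from withdrawn subjects. A fully literal reading would also exclude anyone without a CT, which the authors can hardly have intended. This makes the harmful reading less likely in practice. It does not remove the contradiction, because the plan states no precedence.

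A reader might infer that the plan selectively removes treatment failures and so biases the result in a known direction. The documents do not support that. The same sentence can remove successes, for whom the shift runs the other way, and equal removal of both leaves the difference unchanged. Nor do the documents name a mechanism for unequal exclusion between blinded arms.

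A reader might also infer that rescue antibiotics go unrecorded after withdrawal, because 4.4.2 asks for swabs or symptom data and does not name antibiotic use. That is largely answered elsewhere: 3.2 counts antibiotics during or after irrigation, 5.6 sends worsening subjects back to the same clinic, and 6.5 compiles oral antibiotic use.

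Finally, the illustrated shifts are modest beside the planned precision. Excluding 25% to 50% of failures moves SNOT-22 by about 0.6 to 1.4 points, against a half-width of about 8 to 10. The 100% row needs every failure to be withdrawn, incomplete and excluded, which the discretionary wording makes unlikely. This stands as a limit on the likely size.

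**Conclusion.** The concern holds as a contradiction over who is analysed, joined to a withdrawal rule under which exclusion can depend on outcome. The contradiction is certain from the text and needs no assumption. The bias is not quantified by the documents: its size and direction are unknown. The illustrative range for partial exclusion, 8.6 to 10.6 points around an assumed true difference of 10, rests on the assumed SD for change, effect, cutoff, failure rate and exclusion shares, and on equal exclusion in both arms. It shows that the shift can go either way, not how large it will be. This should be corrected before unblinding, so that the choice of rule cannot follow the results. The sample-size figure in 6.4 is not in question.

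**What to change.** 1. Delete the last sentence of 4.4.2, so that 6.5 and 6.6 govern.
2. In 4.4.1, let persistent symptoms, rescue or non-adherence end use of the irrigant but not follow-up. Only withdrawal of consent ends follow-up. When to stop the irrigant stays a clinical decision.
3. State that every rescued subject stays in the analysis and that the rescue counts as an event on the antibiotic outcome, as 3.2 already implies.

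A sensitivity analysis that uses rescue dates to handle later SNOT-22, endoscopy and culture values is optional. It is a reasonable preference, not the correction of an error, and would need the antibiotic start date on the CRF.

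The cost is amendment wording and some effort to retain subjects. The section 6 table already lists SNOT-22, endoscopy and culture as clinical care at weeks 4 and 12, so no visits are added. However, 3.1 makes the swab conditional on pus and lists no endoscopy at week 12, so obtaining both from everyone may mean some extra work. Values after rescue will also reflect oral antibiotics. If these improved SNOT-22 by 5 to 15 points in rescued subjects (assumed) and rescue were 40% v 20%, the difference would shrink by (0.40 − 0.20) × 5 to 15, that is 1 to 3 points, relative to the difference without rescue.
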